1 PROTOCOL REVISION HISTORY

Version/Date	Description
ARQ-151-101 17 October 2017	Original Protocol
ARQ-151-101 Amendment 1.0 06 December 2017	
Added Protocol Revision History section.Added footnote “k” to the Study Events Flowchart for Cohort 2 under Schedule of Visits and Assessments to allow a window for follow-up visits.Revised Inclusion Criterion #7 to more completely define Women of Non-Child Bearing Potential to include those who are post-menopausal and surgically sterile.Revised Exclusion Criterion #12 to clarify the washout period for excluded biologic medications and to update the washout period for investigational medications.Updated Ethics Review Board information to include information relevant to clinical studies performed in the US.Editorial and administrative changes throughout the protocol to clarify language and formatting to improve readability.
ARQ-151-101 Amendment 1.1 27 February 2018	
This amendment applies only to the US site to add optional dermal imaging assessment (photography).Revised Study Events Flowchart for Cohort 2 under Schedule of Visits and Assessments to show optional photography for Baseline, Visit 3, Visit 4, and Visit 6 for US site.Revised footnote “c” of the Study Events Flowchart for Cohort 2 under Schedule of Visits and Assessments to show photography assessment visits for Canadian (Baseline and Visit 6 only) and US sites (Baseline, Visit 3, Visit 4, and Visit 6).Revised section 8.13.2 Dermal Imaging to show photography assessment visits for Canadian (Baseline and Visit 6 only) and US sites (Baseline, Visit 3, Visit 4, and Visit 6).
ARQ-151-101 Amendment 2.0 19 March 2018	
This amendment increases the number of optional dermal photography assessments from two to four and applies to all sites participating in dermal imaging (both Canadian and US).Revised Study Events Flowchart for Cohort 2 under Schedule of Visits and Assessments to show optional photography for Baseline, Visit 3, Visit 4, and Visit 6 for all sites.Revised section 8.12.1 Screening to indicate four rather than three investigational centers participating in dermal imaging.Revised section 8.13.2 Dermal Imaging to show photography assessment visits for all photography sites at Baseline, Visit 3, Visit 4, and Visit 6.

5 SYNOPSIS

Compound:	ARQ-151 cream 0.15 % and ARQ-151 cream 0.5%
Clinical Indication:	Chronic Plaque Psoriasis
Study Phase and Type:	A Phase 1/2a Single Dose and 28-day Parallel Group, Double Blind, Vehicle-Controlled Study of the Safety, Pharmacokinetics and Efficacy of ARQ-151 cream 0.5% and 0.15% in Adults with Mild to Moderate Chronic Plaque Psoriasis
Study Objectives:	
1. To assess the safety and PK of a single dose application of ARQ-151 cream 0.5% to 25 cm² of psoriatic plaque(s) (Cohort 1)2. To assess the safety, pharmacokinetics and efficacy of ARQ-151 cream 0.5% vs. vehicle and ARQ-151 cream 0.15% vs vehicle applied QD x 28 days to individuals with 0.5% to 5.0% BSA of chronic plaque psoriasis (Cohort 2)
Summary of Study Design:	
There are 2 cohorts of subjects.
 
Cohort 1 is a single dose study to 25 cm² of psoriatic plaque(s) in 8 psoriasis subjects. Cohort 1 subjects will then be enrolled, if they meet entry criteria, into Cohort 2 of the study.
 
Cohort 2 is a parallel group, double blind, vehicle controlled study in which ARQ-151 cream 0.5%, ARQ-151 cream 0.15% or vehicle cream is applied QD x 28 days to subjects with at least 0.5% BSA of chronic plaque psoriasis; area for application will not exceed 5.0% BSA.

Blinding:	
The single dose assessment (Cohort 1) to 25 cm² of psoriatic plaque(s) is open label.
 
The parallel group study (Cohort 2) is double blind and vehicle controlled.

Countries:	Canada (Cohorts 1 and 2) and United States (Cohort 2 only)
Number of sites:	7 sites in Canada; 1 site in the United States.
Study Population:	Subjects will be adults, male and female (>18 y/o). Cohort 1 subjects will have at least 25 cm ² of chronic plaque psoriasis; Cohort 2 subjects will have 0.5 – 5.0% total BSA of chronic plaque psoriasis and at least one target plaque of psoriasis at least 9 cm ² in size and with a TPSS ≥ 4.
Number of Subjects:	
1. Cohort 1 = Up to 8 subjects2. Cohort 2 (can include Cohort 1 subjects) = 84 subjects; randomized 1:1:1 to ARQ-151 cream 0.5%: ARQ-151 cream 0.15%: vehicle/placebo. Total subjects in both cohorts = 84-92.

Duration of Participation for Subjects:	
1. Cohort 1: 22 days (Screening, Day 1, Day 2 and Day 8). If subjects roll into Cohort 2, then total study duration prior to start of Cohort 2 is approximately 22 days. Screening is up to 2 weeks.2. Cohort 2 (not in Cohort 1): Screening (up to 6 weeks) + Treatment phase and follow-up (5 weeks), 77 days.
Study Products:	ARQ-151 cream drug product will be supplied as a 0.15% and 0.5% cream. Matching vehicle cream will contain only excipients of ARQ-151 cream.
Planned Dose Level:	Cohort 1 subjects will receive ARQ-151 cream 0.5% applied to 25 cm ² of psoriatic plaque(s). Cohort 2 subjects will receive ARQ-151 cream 0.15% or 0.5% or matching vehicle cream applied to all psoriatic lesions up to an area of 5.0% BSA (if subject rolled over from Cohort 1, lesions treated in Cohort 1 can also be treated in Cohort 2).
Safety Assessments:	Safety will be monitored through application site assessments, safety labs and AEs.
Safety Analysis:	
The following analyses will be performed; however, no formal inferential statistics will be done on safety assessments.
 
Descriptive statistics will be calculated for quantitative safety data and frequency counts will be compiled for classification of qualitative safety data.
 
Adverse Events: A subject-by-subject treatment-emergent AE (TEAE) data listing, including verbatim term, preferred term, treatment, severity, and relationship to study drug, will be provided. The number of subjects experiencing AEs and number of AEs will be summarized by treatment using frequency counts.
 
Medical History and Physical Examinations: Medical history will be listed by subject. Physical examinations will be performed at screening, baseline and end-of-study.
 
Clinical Laboratory Results: Routine blood chemistries and 12-lead ECGs will be obtained throughout the study.

Efficacy Analysis	
The single dose Cohort 1 will have analyses only for safety and pharmacokinetics.
 
The parallel group assessment (Cohort 2) will have analyses for safety, pharmacokinetics, and efficacy.
 
In the parallel group assessment (Cohort 2), the Primary Efficacy Endpoint will be:
 
• Difference in mean percent change from baseline at week 4 in the product of: [Target Plaque Severity Score (TPSS) x Target Plaque Area (TPA)] (TPSS x TPA) between each dose concentration level of ARQ-151 cream and vehicle control. This will be assessed as a sum of up to 3 target plaques per subject. 
The secondary efficacy endpoints will include:
 
1. Difference in mean percent change from baseline at weeks 1, 2 and 3 in TPSS x TPA between each dose concentration level of ARQ-151 cream and vehicle control. This will be assessed as a sum of up to 3 target plaques per subject.2. Difference in mean percent change from baseline at weeks 1, 2, 3 and 4 in TPSS between each dose concentration level of ARQ-151 cream and vehicle control. This will be assessed as a sum of up to 3 target plaques per subject.3. Difference in mean percent change from baseline at weeks 1, 2, 3, and 4 in TPA between each dose concentration level of ARQ-151 cream and vehicle control. This will be assessed as a sum of up to 3 target plaques per subject.
Pharmacokinetic Sample Collection: (Cohort 1 n = up to 8; Cohort 2 n = 45)	
1. Cohort 1: PK draws will be done at 1, 2, 4, 6 and 24 hours after ARQ-151 cream 0.5% application to 25 cm² of psoriatic plaques2. Cohort 2: PK draws will be done on day 1: 1, 2, 4 and 6 hours; day 14: pre-dose (trough) and 1-hour post-dose; and day 28: pre-dose (trough), 1, 2, 4, 6 and 24 hours post-dose

Statistical Analysis:	
Four analysis populations will be defined:
 
• Safety population will include all subjects who are enrolled and received at least one confirmed dose of study medication; this population will be defined separately for each cohort.• Modified Intent-to-Treatment (mITT) population will include all subjects who are in the safety population for Cohort 2 with at least one post-baseline efficacy evaluation.• Per-Protocol (PP) Population will include all subjects who are in the safety population for Cohort 2, were at least 80% compliant with study medication, and showed no other serious deviations from the study protocol.• PK population will include all subjects receiving the active drug with sufficient plasma concentrations of ARQ-151 cream to define a profile, as determined by the pharmacokineticist; this population will be defined separately for each cohort. 
The primary endpoint of mean percent change from baseline at Week 4 in TPSS x TPA will be analyzed using a mixed model for repeated measures (MMRM). The difference between treatment groups in TPSS x TPA at Weeks 1, 2, and 3 will also be analyzed using the MMRM. Descriptive statistics will be provided for observed and percent change from baseline in TPSS x TPA at Weeks 1, 2, 3, and 4. A comparison of changes in TPSS and TPA between treatment groups will be analyzed similarly to TPSS x TPA.

------------------------------	---

6 SCHEDULE OF VISITS AND ASSESSMENTS

STUDY EVENTS FLOW CHART: COHORT 1; SINGLE DOSE APPLICATION TO 25 cm²

Study Procedure	Days	Screening	Day 1	Day 2	Day 8
	Weeks	2 weeks			
Informed consent		X			
Medical history		X			
Physical examination ^a		X	X		
Hematology, Serum Chemistries, and Urine Analysis		X		X	
Urine Drug Screen		X			
I/E criteria		X	X		
Vital signs, height, weight		X	X		
Urine pregnancy test ^b		X	X		
Resting 12-lead ECG		X			
ARQ-151 cream application ^c			X		
PK sampling ^d			X	X	
Application Site Reaction Assessment			X	X	
Adverse events assessments			X	X	
Concomitant medications		X	X	X	
Telephone Follow-up ^e					X

^a Limited physical examination: skin, lungs, and heart only

^b A urine pregnancy test will be administered to all females of child-bearing potential. A negative result is required for continued participation in the study, and results must be available prior to dispensing of study drug.

^c ARQ-151 cream application to 25 cm² of target plaque(s)

^d PK sampling: 1, 2, 4, 6 (±10 minutes for 1, 2, 4 and 6 hour collections) and 24 hours (± 1 hour) after ARQ-151 cream application to 25 cm² of psoriatic plaque(s)

^e Telephone call to the subjects for follow up on any continuing adverse events related to study drug. Telephone call will also assess any emergent adverse event post Day 1 ARQ-151 cream application. Any emergent AEs will be followed in the clinic at the investigator's discretion for up to one month until resolved or otherwise judged as clinically stable.

**STUDY EVENTS FLOW CHART: COHORT 2; 28 DAY APPLICATION TO 0.5 – 5% BSA;
DOUBLE BLIND, PLACEBO CONTROLLED**

Study Procedure	Screen Visit 1	Baseline Day 1 Visit 2	Week 1 Day 7 ^k Visit 3	Week 2 Day 14 ^k Visit 4	Week 3 Day 21 ^k Visit 5	Week 4 Day 28 ^k Visit 6	Week 4 Day 29 ^k Visit 7	Week 5 Day 35 ^k
Weeks	-6	0	1	2	3	4		
Informed consent	X							
Medical history	X							
Physical examination ^a	X	X				X		
I/E criteria	X	X						
Hematology, Serum Chemistries, and Urine Analysis	X	X		X		X		
Urine Drug Screen	X							
Vital signs, weight, height	X	X	X	X	X	X		
TPSS x TPA measurements ^b	X	X	X	X	X	X		
Application Site Reaction Assessment		X	X	X	X	X		
Depressive Symptomatology Questionnaire	X			X		X		
Optional Photography ^c		X ^c	X ^c	X ^c		X ^c		
Urine pregnancy test ^d	X	X	X	X	X	X		
Resting 12-lead ECG	X	X				X		
PK sampling ^e		X		X		X	X	

**STUDY EVENTS FLOW CHART: COHORT 2; 28 DAY APPLICATION TO 0.5 – 5% BSA;
DOUBLE BLIND, PLACEBO CONTROLLED (Continued)**

Study Procedure	Screen	Baseline	Week 1	Week 2	Week 3	Week 4	Week 4	Week 5
Weeks	-6	0	1	2	3	4		
Vehicle Application in Clinic (subject training) ^f			X ^f		X ^f			
Drug/Vehicle Application in Clinic ^g		X ^g		X ^g		X ^g		
ARQ-151 cream/Vehicle application at home		X	X	X ^h	X	X ^h		
Dispense study medication		X	X	X	X			
Weigh study medication		X	X	X	X	X		
Dispense/Review Diary		X	X	X	X	X	X ⁱ	
Adverse events assessments		X	X	X	X	X		
Concomitant medications	X	X	X	X	X	X		
Optional Skin biopsy ^j						X		
Telephone follow up ^j								X

^a Limited physical examination: skin, lungs, and heart only

^b Target Plaque Severity Score: Sum of erythema, induration, and scaling each scored 0-4 (maximum score = 12). Target plaque area = Longest diameter (cm) x Widest perpendicular diameter (cm). Up to three target plaques will be chosen, each at least 9 cm². The target plaques must each have a TPSS ≥ 4 . Subjects must have at least one target plaque.

^c Photography will be at selected investigational sites. Photography will be optional and confined to the target lesions. All efforts will be made to de-identify the subjects.

^d A urine pregnancy test will be administered to all females of child-bearing potential. A negative result is required for continued participation in the study, and results must be available prior to dispensing of study drug at each visit.

**STUDY EVENTS FLOW CHART: COHORT 2; 28 DAY APPLICATION TO 0.5 – 5% BSA;
DOUBLE BLIND, PLACEBO CONTROLLED (Continued)**

- e PK draws on day 1: 1, 2, 4 and 6 hours (\pm 10 minutes for 1, 2, 4 and 6 hour collections); day 14: pre-dose (trough) and 1-hour (\pm 10 minutes) post-dose; and day 28: pre-dose (trough), 1, 2, 4, 6 (\pm 10 minutes for 1, 2, 4 and 6 hour collections); and 24 hours (\pm 1 hour) post-dose for analysis. PKs will be collected from at least 45 volunteer subjects; PK collections will continue until PKs have been collected from 15 subjects in each treatment group.
- f Vehicle application training post baseline will be conducted as needed on Visits 3 (week 1) and 5 (week 3).
- g Drug or vehicle will be applied in clinic.
- h Visits 4 (week 2) and 6 (week 4) only: ARQ-151 cream or vehicle application will be done at home in the morning of Days 13 and 27 and in the morning at the clinic on PK collection Days 1, 14 and 28. ARQ-151 cream or vehicle will not be applied in the evening of Days 13 and 27.
- i 4 mm skin punch biopsy for analysis of Roflumilast and metabolites (n = 15 for analysis). Tissue will be collected from at least 15 volunteer subjects; tissue collection will continue until samples have been collected from 5 subjects in each treatment group.
- j Telephone call to the subjects for follow up on any continuing adverse events related to study drug. Telephone call will also assess any emergent adverse event post Visit 6. Any emergent AEs will be followed in the clinic for up to one month at the investigator's discretion until resolved or otherwise judged as clinically stable.
- k Follow-up visits should occur within +/- 1 day of the targeted date.
- l For those subjects participating in the PK assessment, diary is completed by subject and reviewed by study staff during visit (Possible Side Reactions / Comments Section of the diary).

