8.5 Overall Study Design and Plan

There are 2 cohorts of subjects:

Cohort 1 is a single dose study to 25 cm² of psoriatic plaque(s) in up to up to 8 psoriasis subjects. Cohort 1 subjects may then be enrolled into Cohort 2 of the study if all admission criteria are met at the Baseline Visit (Day 1, Visit 2, per Cohort 2). In this case, the same plaque(s) treated in the Cohort 1 study may also be treated in Cohort 2.

Cohort 2 is a parallel group, double blind, vehicle controlled study in which ARQ-151 cream 0.5%, ARQ-151 cream 0.15% or vehicle cream is applied QD x 28 days to subjects with between 0.5% to 5.0% BSA of chronic plaque psoriasis.

Including both Cohorts, a total of up to 92 subjects will be enrolled at 7 study sites in Canada and 1 site in the U.S. Subjects will be adult (≥ 18 y/o) males or females with chronic plaque psoriasis. For inclusion into Cohort 2, subjects must have at least 1 target plaque of at least 9 cm² in size with TPSS ≥ 4 . While 1 target plaque is minimally acceptable, it is strongly recommended that 2 or 3 target plaques be identified, if present, meeting these criteria. Target plaques may be on the knees and/or elbows, but priority should be given to identifying target lesions in other areas. All psoriasis lesions on a subject will be treated in this Cohort except for those on the face, scalp, intertriginous areas, palms and soles.

Subject Participation

Cohort 1: This cohort involves a minimum of three clinic visits including Screening, Baseline, one follow-up visit (24 hours after the baseline visit) and one follow up telephone call 7 days after the follow up visit. Subjects may be asked to return for additional visits(s) if an adverse reaction occurs. The interval between the Screening and Baseline visits could be up to 14 days, therefore the anticipated maximum duration of subject participation in Cohort 1 is 22 days.

Cohort 2: This cohort involves a minimum of seven clinic visits including Screening, Baseline and four visits at Week 1, Week 2, Week 3 and Week 4 of treatment and a day 29 visit for a final PK collection. A follow-up telephone call with subjects will occur at week 5 to assess any reactions to discontinuing drug product and will decide upon disposition of any ongoing adverse events.

The interval between the Screening and Baseline visits could be up to 6 weeks, therefore the anticipated maximum duration of subject participation in Cohort 2 is 77 days.

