8.11 Treatments

8.11.1 Drug Administration

Cohort 1: ARQ-151 cream 0.5% will be applied by site personnel to 25 cm² of psoriatic plaque(s) (more than one plaque may be identified for a total area of 25 cm²).

The study sponsor or its representative will ensure the study staff can demonstrate proper dosing for Cohort 1 at the Site Initiation Visit. Study staff will be trained to ensure a unit dose (a pea-sized amount of ARQ-151 cream vehicle) is properly squeezed from the vehicle training tube and applied as a thin film and rubbed in using the index and middle finger, rubbing in thoroughly but gently, until the 'white' has disappeared.

Cohort 2: At the randomization visit, the study staff will demonstrate to the subject how to apply ARQ-151 cream or vehicle using the first tube from the kit that is assigned to the subject at randomization. The study staff will demonstrate application to the subject according to the technique described above. The subject will then practice squeezing a similar amount onto their index and middle finger and apply a thin film to areas to be treated. The study staff will confirm that the subject's application technique is correct.

Re-training will be conducted at subsequent visits (visits 3 and 5) as needed using a vehicle training tube (i.e., if a returned tube weighs substantially more or less than the expected weight).

Subjects will be instructed to apply study medication each evening at least 15 minutes after showering or bathing (if they take an evening shower/bath) and then to not wash areas where ARQ-151 cream or vehicle have been applied until the following morning. Study medication should be applied at least 10 minutes before going to bed.

Each study medication tube will be weighed prior to dispensing at the baseline visit and each follow up visit. Study medication tubes returned by subjects will also be weighed and compliance will be assessed. If the subject's actual use is substantially greater than or less than the expected use, the subject will retrained on the study drug application technique.

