8.15.1 Blood and Skin Sampling and Processing

Blood samples for pharmacokinetic evaluation will be performed as follows:

Cohort 1: PK draws will be done at 1, 2, 4, 6, and 24 hours after ARQ-151 cream 0.5% application to 25 cm² of psoriatic plaque(s).

Cohort 2: PK draws will be done on day 1: 1, 2, 4 and 6 hours; day 14: pre-dose (trough) and 1-hour post-dose; and Day 28: pre-dose (trough), 1, 2, 4, 6 and 24 hours. On days 1, 14, and 28, study medication will be applied in the clinic and blood draws performed subsequently. Subjects will be contacted on days 12 and 26 and reminded to apply their study medication in the morning of days 13 and 27. Study medication will not be applied in the evening of days 13 and 27.

An optional 4 mm diameter punch biopsy will be collected from a target plaque at the Day 28 Visit. The punch biopsy will include the epidermis, dermis, and sub-cutaneous skin layers.

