6.1.7. Derived Variables

- TPSS = sum of erythema (graded 0-4), thickness (graded 0-4), and scaling (graded 0-4) for each target plaque. The sum of TPSS scores of up to 3 target plaques within a visit will be used for analysis.
- TPA (cm^2) = the longest diameter (cm) of the target plaque multiplied by the widest perpendicular diameter (cm) (ie, perpendicular to the longest diameter of the target plaque). The sum of TPA (cm^2) of up to 3 target plaques within a visit will be used for analysis.
- TPSS x TPA = sum of TPSS x TPA of up to 3 target plaques within a visit. Note that TPSS x TPA is calculated for each target plaque before summing up the results for all plaques. If a plaque is resolved after baseline with a score of 0 for all descriptors for TPSS (ie, erythema, thickness, and scaling), TPSS x TPA will be recorded as 0.
- Cream used (g) in a tube = dispensed tube weight (g) – returned tube weight (g).
- Overall cream used (g) = sum of cream used in a tube over all tubes
- Number of doses of study drug = number of expected doses (number of days on study [including BID dosing on Days 1, 14, and 28], where number of days on study is derived as last treatment – first treatment + 1) minus total number of missed doses, as collected in the CRF. Add a 1 for each of the Day 1, 14, and 28 visits that are completed (meaning, study drug discontinuation did not occur until at least the next day; so if a subject finished the study, 3 doses would be added to the final amount).
- Percent compliance (for purposes of determining the PP Population as described in [Section 5](#)) = average of compliance as recorded in the eCRF, calculated as sum of [100% if “Was the subject compliant?” marked Yes in the eCRF or percent compliance as recorded in the eCRF comments when “Was the subject compliant?” is marked as No] / number of non-missing compliance records from the eCRF.
- Quick Inventory of Depressive Symptomatology-Self-Report (QIDS-SR) total score = (highest score on questions 1-4) + item 5 + (highest score on questions 6-9) + item 10 + item 11 + item 12 + item 13 + item 14 + (highest score on questions 15-16). The range for the QIDS-SR total score is 0 to 27.

- QIDS-SR severity level⁴:
 - No depression: total score ≤ 5
 - Mild depression: total score = 6 to 10
 - Moderate depression: total score = 11 to 15
 - Severe depression: total score = 16 to 20
 - Very severe depression: total score ≥ 21

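### SAP 6.1.7 credits every completer with a second dose on Day 28, which the protocol schedule does not support; the protocol never states that the Day 28 clinic dose is the last

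*Protocol*

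**What the plan says.** **Regimen.** Protocol 8.5 sets the regimen: "vehicle cream is applied QD x 28 days to subjects with between 0.5% to 5.0% BSA". The SAP repeats it in 3.1.

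**Time of day.** Protocol 8.11.1 gives the general home instruction: "Subjects will be instructed to apply study medication each evening at least 15 minutes after showering or bathing". Footnote h of the Cohort 2 flow chart (Section 6) places the clinic application in the morning of Days 1, 14 and 28, moves the home dose of Days 13 and 27 to the morning, and adds: "ARQ-151 cream or vehicle will not be applied in the evening of Days 13 and 27". Protocol 8.15.1 says the same: "Study medication will not be applied in the evening of days 13 and 27". Neither place mentions the evenings of Days 1, 14 or 28.

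**Sampling.** Footnote e lists Day 28 draws before the dose and at 1, 2, 4, 6 and 24 hours after it. The last is taken at the Day 29 visit. Protocol 9.4 times samples from the start of drug application.

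**End of treatment.** The flow chart dispenses nothing at Week 4 and shows no tube weighing after it. For PK subjects the diary is looked at once more on Day 29, but footnote l limits this: "reviewed by study staff during visit (Possible Side Reactions / Comments Section of the diary".

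**Dose count.** SAP 6.1.7 takes days on study, "including BID dosing on Days 1, 14, and 28", subtracts missed doses, and adds one for each of those visits completed: "so if a subject finished the study, 3 doses would be added to the final amount". The top exposure category in SAP 7.4 is 24 to 31 doses. SAP Section 10, on changes from the planned analysis, does not mention this count.

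**The concern.** The SAP counts a Day 28 evening dose that the protocol neither schedules nor rules out. A subject or site that follows 8.11.1 literally would dose that evening, because only Days 13 and 27 are excepted. One that follows the once-daily regimen and the dispensing schedule would not. The SAP repeats the once-daily wording and footnote h, so it also conflicts with itself.

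Two outputs are at stake. The first is the exposure summary, which is wrong for every completer if the clinic dose is the last. The second is the Day 28 PK profile. PK is part of the primary objective, this is the only multiple-dose profile, and the Day 29 sample is its only point after 6 hours. The protocol protects the Day 28 trough by cancelling the Day 27 evening dose and reminding subjects on Day 26. It gives the Day 29 sample no such protection.

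**Working it through.** **1. Reproduce the SAP figure.** Days on study = last treatment − first treatment + 1 = 28 − 1 + 1 = 28. Add-on for Days 1, 14 and 28 = 3. Total = 28 + 3 = 31. This matches the upper end of the top category in SAP 7.4, so the SAP does count a Day 28 evening dose.

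**2. Count doses from the protocol calendar, with no dose on the evening of Day 28 and none missed.**

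| Days | Second dose on Days 1 and 14 (assumed) | Strict once daily |
|---|---|---|
| 1 | 2 | 1 |
| 2–12 | 11 | 11 |
| 13 (morning) | 1 | 1 |
| 14 | 2 | 1 |
| 15–26 | 12 | 12 |
| 27 (morning) | 1 | 1 |
| 28 (clinic) | 1 | 1 |
| Total | 30 | 28 |
| SAP overcount | 31 − 30 = 1 (1/30 = 3.3%) | 31 − 28 = 3 (3/28 = 10.7%) |

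The first column is an assumption. The flow chart marks both clinic and home application at Baseline and Week 2, but no protocol sentence specifies two doses on those days.

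**3. Visit window.** Footnote k states: "Follow-up visits should occur within +/- 1 day of the targeted date". With Visit 6 on Day 27, 28 or 29, the SAP formula gives 27 + 3 = 30, 28 + 3 = 31 or 29 + 3 = 32. No category in SAP 7.4 holds 32. The counts 28, 30 and 31 all fall in 24 to 31, so apart from this edge case only the continuous summary changes.

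**4. If an evening dose is applied on Day 28.** Time from that dose to the Day 29 draw = 24 + clinic clock time − evening clock time. The documents give only morning and evening. Assuming a clinic dose at 08:00–10:00 and an evening dose at 20:00–22:00, the interval runs from 24 + 8 − 22 = 10 h to 24 + 10 − 20 = 14 h (12 h for 09:00 and 21:00). The interval from the clinic application remains 24 h.

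**5. Direction and possible size of the PK effect.** An intervening dose can only raise the 24-hour concentration (C24) and the 6–24 h part of the AUC. The documents give no half-lives, so the size can only be illustrated. The illustration is a one-compartment model with first-order absorption and equal doses on the 30-dose calendar, an evening dose at +12 h, and the linear trapezoid over the scheduled times. Assumed elimination half-lives are 8, 12, 24 and 48 h and absorption half-lives 2, 6, 12 and 24 h (16 combinations).

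- C24 is multiplied by 1.09 to 3.30.
- AUC0-24 rises by 3% to 32%: under 10% in 6 combinations, at least 20% in 5.
- Without the extra dose, the 6–24 h segment is 69% to 75% of AUC0-24.

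These are outcomes over an assumed grid, not likelihoods. PK is planned in 15 subjects per group, so at most about 2 × 15 = 30 active-arm subjects could be affected.

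**The case against.** The best defence is that treatment plainly ends at Visit 6. Besides the once-daily regimen and the dispensing and weighing schedule, the flow chart has no adverse event or concomitant medication assessment after Visit 6 other than the telephone call. Protocol 8.5 describes the Week 5 call as covering reactions to stopping the product. Footnote h attributes the Week 4 home dose to the morning of Day 27. The evenings of Days 13 and 27 are excepted because the next morning's sample is a trough, which does not imply that a dose was intended on the evening of Day 28. All of this stands and makes the extra dose the less likely reading. It also makes the SAP count wrong.

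The SAP rule might be said to correct itself, since the add-on requires that discontinuation came no earlier than the next day. That could deny the Day 28 credit to someone whose last dose was that morning. But the same rule then gives all three doses to a subject who finishes.

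Two stronger readings are tempting and unsupported. A reader might infer that the Day 29 sample is mislabelled and is really a 12-hour sample. It is not: 9.4 times samples from drug application, footnote e puts the draw in the Day 28 series, and it remains 24 h after the clinic dose. A reader might also take 30 as the true dose total. It depends on evening doses on Days 1 and 14 that no protocol sentence specifies.

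Finally, the sampling manual (9.4) and the PK report (SAP 11.1) are separate documents and may already deal with an intervening dose. Neither would correct the exposure count in SAP 6.1.7.

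**Conclusion.** SAP 6.1.7 is wrong as written, with a linked gap in protocol footnote h and 8.15.1. The schedule indicates that the Day 28 clinic dose is the last, no sentence says so, and the SAP counts one more.

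If the clinic dose is last, a 28-day completer with no missed doses is overcounted by one dose, assuming evening doses on Days 1 and 14, or by three under strict once-daily dosing. The formula can also reach 32, outside the last category. If subjects do dose that evening, the SAP count for Day 28 is right, but C24 and the 6–24 h part of AUC are biased upward by an amount the documents cannot determine.

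The impact is minor. The exposure table and PK are descriptive, and overstated systemic exposure errs on the cautious side for safety. The efficacy analyses and the 0–6 h PK data are unaffected. So is the per-protocol population, which uses compliance recorded in the eCRF, not this count. The reason to act is that the correction is small and both documents should describe the same regimen.

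**What to change.** 1. **Protocol footnote h and 8.15.1:** state that no cream is applied between the Day 28 clinic dose and the Day 29 draw. Repeat the sentence in the SAP copy of the footnote.
2. **SAP 6.1.7:** remove the automatic Day 28 add-on. Count a second dose on Day 1, 14 or 28 only where the diary dose times show that it was applied. With no dose on the evening of Visit 6, the largest count is then 29 + 2 = 31, which fits the existing category.
3. **Day 29 visit:** check the diary for a dose on the evening of Day 28. If there was one, count it for that subject, flag the sample, and do not use it as a 24-hour post-dose value in the Day 28 AUC.

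**Cost.** One sentence in two protocol places, one SAP rule, one diary check and one line in the PK handling rules. Under 8.11.3 the diary already records the date and time of each dose, so subjects record nothing new. SAP 6.1.7 mentions only missed doses as collected in the CRF, so if dose times are not in the database, entries for three evenings would need to be transcribed. The scientific downside is that a flagged subject keeps only the 0–6 h Day 28 profile. That affects nobody if the clinic dose was last, and at most about 30 active-arm PK subjects if all dosed that evening.
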